4.3.2. Post-Baseline Analyses of Continuous Variables

For each continuous response variable, visit-specific analyses will be performed for the visits where the variable was scheduled to be measured. If a patient has no post-baseline measurements of a variable, the patient will not be included in the visit-specific analyses of that variable. Analyses of change and percent change from baseline to specific visits will have the same requirements plus the additional constraint that the patient has a baseline measurement of the variable.

The default analysis model for continuous response variables expected to be normally distributed will be a mixed-effects model for repeated measures (MMRM) using restricted maximum

likelihood (REML). The MMRM model will be used to analyze changes from baseline with the baseline value as the covariate. The model will include fixed effects for treatment, visit, treatment-by-visit interaction, the baseline as a covariate, and the patient as a random effect. An unstructured covariance structure will be used to model the within-patient errors. This analysis includes visits where the continuous response variable was scheduled to be measured.

If this analysis fails to converge, the following covariance structures will be tested in order:

- toeplitz with heterogeneity
- autoregressive with heterogeneity, by visit
- compound symmetry with heterogeneous variances, by visit
- toeplitz,
- autoregressive
- compound symmetry without heterogeneous variances, by visit

The first covariance structure that converges will be used. The Kenward-Roger approximation will be used to estimate denominator degrees of freedom. Significance tests will be based on least-squares mean (LS Mean) using Type III sum of squares.

Summary statistics will include sample size, mean, SD, median, 10th and 90th percentiles for both the actual and the change from baseline measurements. Least-squares mean (LS Mean) and standard error (SE) derived from the model will also be displayed for the change from baseline measurement. Treatment comparisons will be displayed showing the treatment difference LS Mean and the 95% confidence limits along with the p-value.

For continuous lab measurements, an analysis of variance (ANOVA) on rank-transformed data will be used and p-values for the difference between dulaglutide and placebo will be reported, unless stated otherwise. The model includes treatment. Treatment group comparisons will be performed with no multiplicity adjustment. Categorical laboratory measures will be analyzed using Chi-square test or Fisher's exact test.

In situations where the continuous response variable will be expected to violate the assumption of normality, Wilcoxon's rank sum test will be used. Such situations will be appropriately identified throughout this SAP. Between-treatment comparisons will be assessed using the p-value, and within-treatment changes will be assessed using the p-value from the signed rank test. Summaries for these variables will include descriptive statistics: number of patients, median, and 25th and 75th percentiles. In addition, the Hodges-Lehman estimator of the treatment contrast will be provided.

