For continuous measures, analysis of covariance (ANCOVA) and or mixed-effects model for repeated measures (MMRM) will be used to analyze changes from baseline with the baseline value as the covariate. The MMRM model will include fixed effects for treatment, visit, treatment-by-visit interaction, the baseline as a covariate and the patient as a random effect. Summary statistics will include sample size, mean, standard deviation, median, 10th and 90th percentiles for both the actual and the change from baseline measurements. Least-squares mean (LS Mean) and standard error derived from the model will also be displayed for the change from baseline measurement. Treatment comparisons will be displayed showing the treatment difference LS Mean and the 95% confidence limits along with the p-value.

[figure not shown]
For continuous lab measurements, an analysis of variance (ANOVA) on ranks will be used and p-values for the difference between the dulaglutide and placebo will be reported.

For categorical measures, summary statistics will include sample size, frequency, and percentage. Frequencies will be analyzed using Chi-square tests if the expected count is at least 5, in at least 80% of the cells, otherwise a Fisher's exact Test will be used.

All analyses will be implemented using SAS® Version 8.2 or higher.

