4.15.2. Analyses of Cognitive Function and Erectile Dysfunction

Cognitive function will be assessed in all randomized patients using the MoCA instrument and the DSST at baseline (Visit 3) and after 24, and 60 months of treatment and at the final visit.

The MoCA is a cognitive screening test designed to detect mild cognitive impairment (Nasreddine et al. 2005). It assesses different cognitive domains: attention and concentration, executive functions, memory, language, visuoconstructional skills, conceptual thinking,

calculations, and orientation. It will take approximately 10 minutes to complete the test. The total possible score is 30 points; a score of 26 or above is considered normal.

The DSST is an attention-demanding psychomotor component of the Wechsler Adult Intelligence Scale (Kuo et al. 2007). The patient is given a symbol-digit code in which each of the digits 1 through 9 is paired with a different symbol. Below the code, a series of symbols selected from those in the code are presented in an irregular order. The patient is instructed to draw the symbol that matches the number and to complete as many correct symbols as possible within a 120-second test period. The DSST score is the number of correct symbol-number matches. The number of matches attempted will also be recorded.

Analyses of the last score for the MoCA and the DSST, and visit-specific analyses will be performed using MMRM (Section 4.3.2) for each of these continuous test scores. The analysis will be based on change from baseline. Patients will be required to have a baseline and at least one post-baseline score to be included in these analyses.

The MoCA score is a continuous variable with a range of [0, 30]. It will also be analyzed as a categorical variable using the categories: below the threshold for normal cognitive function (that is, mild cognitive dysfunction, MoCA score <23 for Korea and MoCA score <26 for all other countries), and above the evaluation threshold (that is, normal cognitive function, MoCA score \geq 23 for Korea and MoCA score \geq 26 for all other countries). The number and proportion of patients in each category at each visit will be compared between treatment group using a Chi-square test or Fisher's exact test.

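### SAP 4.3.2 gives the default MMRM a patient random effect it cannot identify alongside an unstructured covariance, and SAP 4.15.2 applies that model to a single last cognitive score

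*SAP*

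**What the plan says.** SAP 4.3.2 defines the default analysis of normally distributed continuous responses as an MMRM fitted by REML. The mean model is ordinary: "The model will include fixed effects for treatment, visit, treatment-by-visit interaction, the baseline as a covariate". The covariance is described in two adjoining statements: "the baseline as a covariate, and the patient as a random effect. An unstructured covariance structure will be used to model the within-patient errors". The rule for departing from it rests on convergence alone: "If this analysis fails to converge, the following covariance structures will be tested in order", and "The first covariance structure that converges will be used". The list runs: heterogeneous Toeplitz, heterogeneous autoregressive, heterogeneous compound symmetry, then homogeneous Toeplitz, autoregressive and compound symmetry. Kenward-Roger degrees of freedom are specified.

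The SAP uses this model for HbA1c, weight and waist/hip ratio (4.15.1), MoCA and DSST (4.15.2), IIEF (4.15.3) and vital signs (4.17.4).

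SAP 4.15.2 says the cognitive tests are given "at baseline (Visit 3) and after 24, and 60 months of treatment and at the final visit", and then: "Analyses of the last score for the MoCA and the DSST, and visit-specific analyses will be performed using MMRM". The last score is therefore listed in addition to the visit-specific analyses. Protocol 12.2.10 had planned ANCOVA for the last DSST score. The SAP revision history records that Version 3 substituted MMRM for ANCOVA for these scores.

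Protocol 12.2.1 also describes an MMRM with "the baseline as a covariate and the patient as a random effect", but states no error covariance structure.

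**The concern.** A patient random effect adds the same variance to every element of a patient's covariance matrix. An unstructured error matrix can already take any value in every element. Having both leaves the optimiser a direction along which the likelihood is flat. That matters here because the plan chooses the covariance structure by whether the fit converges. A redundant parameter could make the first-choice model fail, and the analysis would then move to another structure although nothing in the data called for it. Different programmers could also end with different structures for one outcome; SAP 4.2 allows analyses by the ISAC, the CRO and the sponsor.

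The last-score problem is separate. One record per patient contains no repeated measures, so the assigned model has nothing to model. The value may come from month 24, month 60 or the final visit. If cognition declines with time, patients last tested early look better, and the comparison favours the arm with more early loss.

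**Working it through.** The plan gives no figure to reproduce, so the check is of the model itself.

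**1. Redundancy of the default model.** Let V be the marginal covariance over T visits, s² the patient variance, J the matrix of ones and R the error covariance. Then V = s²J + R. V has T(T+1)/2 distinct elements, and an unstructured R uses that many parameters before s² is added.

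| T | Distinct elements of V | Parameters, R + s² | Rank | Deficit |
|---|---|---|---|---|
| 3 (MoCA, DSST, IIEF) | 6 | 7 | 6 | 1 |
| 7 (illustrative) | 28 | 29 | 28 | 1 |
| 8 (illustrative) | 36 | 37 | 36 | 1 |

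For a given V, every s² from 0 to 1/(1′V⁻¹1) gives a valid R and the same likelihood. For an assumed V with SD rising linearly from 4 to 8 over 7 visits and correlation 0.9 per lag, that range is 0 to 15.8.

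**2. Effect on the treatment comparison.** In simulated data (400 patients, T = 3), V was held fixed and s² set to 0, 0.3, 0.6, 0.9 and 1.2. At all five values the REML log-likelihood was −1495.202859, the last-visit treatment effect 0.576243 and its standard error 0.245694. Only the split of variance is undefined. The marginal covariance and the treatment effects are identified.

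**3. The fallback list, with the random effect retained.** Adding s²J to a homogeneous Toeplitz or compound-symmetry matrix gives another matrix of the same kind, so these two also have deficit 1. Heterogeneous Toeplitz, heterogeneous autoregressive, heterogeneous compound symmetry and homogeneous autoregressive have deficit 0. The first three fallbacks are therefore identifiable, and they let the variance differ by visit.

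**4. If an equal-variance structure were nevertheless reached.** With complete data, the model-based last-visit standard error is off by the ratio of pooled SD to last-visit SD.
- SD 4 to 8: mean variance 37.78, pooled SD 6.15, ratio 6.15/8 = 0.77, so 23% too small. Type I error 2[1 − Φ(1.96 × 0.768)] = 13%.
- SD 5 to 7: mean variance 36.44, pooled SD 6.04, ratio 6.04/7 = 0.86, so 14% too small. Type I error 9%.

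The SDs are assumptions; the documents give none.

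**5. The last score as a model.** No patient contributes two visits, so all 3 off-diagonal elements of the 3 × 3 unstructured matrix have no data behind them. With visit terms dropped, the log-likelihood in simulated data was −538.382578 for every split of variance tried. Estimate and standard error were 0.5725 and 0.2313, identical to ordinary ANCOVA.

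**6. Size of the last-score bias.** Bias = decline per year × years earlier × between-arm gap in the share last seen early. Assume a decline of 1 point a year and SD 10. A patient last tested at month 24 rather than at the average follow-up of 6.5 years is seen 6.5 − 2 = 4.5 years earlier. With 4800 per arm, the standard error of the difference is 10 × √(2/4800) = 0.204.
- Gap of 2 percentage points: 1 × 4.5 × 0.02 = 0.09 points, or 0.09/0.204 = 0.44 SE.
- Gap of 0.5 percentage points: 1 × 4.5 × 0.005 = 0.0225 points, or 0.11 SE.

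The Protocol synopsis plans 9500 of 9600 completing: 100/9600 = 1.0% lost over both arms. The 0.15% annual dropout in Protocol 12.1 agrees (0.15% × 6.5 = 0.98%). A 2-point gap would need nearly all 100 non-completers in one arm (100/4800 = 2.1%).

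**The case against.** The strongest reply is that this is loose wording with no consequence. The only mixed-model code in the SAP, for severe hypoglycemia rates in 4.17.1.1, fits visit as an unstructured residual-side effect within patient and has no separate patient effect. The author may have meant the same in 4.3.2. That is plausible and points to the repair, but the code belongs to another analysis and 4.3.2 states both components.

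A reader might infer that the default MMRM results would be biased or invalid. Step 2 shows otherwise: once the model converges, inference is unchanged. Nor do the documents show that it will fail to converge; they show only that failure would be acted on.

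A reader might also take 13% as the expected type I error. It would require the unstructured model and all three heterogeneous fallbacks to fail. Those three are identifiable, so the redundancy gives no reason for them to fail. The 7-visit example also does not describe MoCA, DSST or IIEF, which have three post-baseline occasions.

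A third inference is that Protocol 12.2.1 has the same defect. It does not: a patient random effect with no unstructured error matrix is identifiable.

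On the last score, it is fair to say that the analysis can be computed, because it becomes the ANCOVA that the Protocol planned for DSST, and that visit-specific contrasts at month 60 and the Final Visit are already planned. It is also fair that the Final Visit is event-driven, so even that contrast mixes follow-up times. What stands is that the text names a repeated-measures model for a single value and does not define the last score as a final-visit contrast.

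**Conclusion.** Both points hold as faults of specification, and both are minor. The patient variance in SAP 4.3.2 is not identifiable next to an unstructured error covariance. Treatment estimates and standard errors are unaffected on convergence; the exposure is an unnecessary move down the fallback list, mostly to structures that do little harm. The 23% and 14% understatements of the late-visit standard error belong only to an equal-variance fallback under assumed SDs, and should not be read as the expected effect.

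The last-score analysis in SAP 4.15.2 is a last-observation ANCOVA under another name. Its bias is about 0.02 points (0.11 SE) for a 0.5-point gap in early loss, given the assumed decline and SD. A larger gap could arise from deaths or missed cognitive tests, for which the documents give no figure; planned dropout alone does not support one near 2 points.

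The scope is the additional measures and vital signs, for which SAP 4.3.6.1 makes no multiplicity adjustment. The primary and secondary time-to-event analyses are not touched.

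**What to change.** - **SAP 4.3.2:** delete the phrase making the patient a random effect. State that visit is a repeated (residual-side) effect within patient with unstructured covariance, as in the code in 4.17.1.1. The model then has full rank (6 parameters for 6 elements at T = 3, 28 for 28 at T = 7). Add that sandwich standard errors will be used if an equal-variance fallback is reached. These would replace the Kenward-Roger adjustment, a negligible loss at about 9600 patients.
- **SAP 4.15.2:** drop the separate last-score analysis and rely on the planned month-60 and Final Visit MMRM contrasts, or keep it and label it a supportive last-observation ANCOVA.
- **Protocol 12.2.1:** no correction needed beyond aligning its wording with the SAP.

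The cost is a few lines of SAP text and simpler code. No new data are needed.

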#### **12.2.9.4. Analysis of Laboratory Analytes**

Laboratory measurements collected at scheduled visits will be listed by patient by visit using all randomized patients. An additional listing will be presented for all laboratory measurements that are outside the SI units (International System of Units) normal range. Baseline for calcitonin, ALT, and hemoglobin A1c, will be Visit 1 and for serum creatinine, urine ACR and lipids will be Visit 3. All summary analyses will be based on the ITT population. Laboratory measurements that fall within a visit window will be associated with that visit. The laboratory measurement within the window that was taken closest to the visit date will be representative of that patient's lab value for that visit.

Unless otherwise specified, continuous laboratory measures will be analyzed using an ANOVA model on the rank-transformed data. The model includes treatment. Treatment group comparisons will be performed with no multiplicity adjustment. Categorical laboratory measures will be analyzed using Chi-square tests or Fisher's exact tests. For lipids (total cholesterol, LDL-C, HDL-C, triglycerides, and non-HDL-C) the summary analysis will be conducted based on the percentage change from baseline using an ANOVA model described above. The change from baseline will be used for the ratio of total cholesterol to HDL-C.

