For subgroup analyses, all tests of interactions between treatment groups and other factors will be conducted at a nominal 2-sided alpha level of 0.10 and will be deemed to be exploratory. No adjustment for multiplicity will be performed unless otherwise specified.

Countries in similar geographic regions with <10 patients will be pooled in order to achieve a pooled country of at least 10 patients. All analyses using country in the model will use pooled country, unless otherwise specified. The final pooling by country and geographic region will be specified prior to data lock.

The baseline is Visit 3. If baseline data are missing, the last measurement taken prior to this visit will be used for the baseline measurement.

The primary analysis and key secondary CV endpoint analyses will be based on adjudicated events that occurred after randomization (Visit 3). Sensitivity analyses may be conducted

including events reported by investigators or events identified through safety reviews, to assess their impact on the primary analysis results.

All analyses will be implemented using SAS Version 8.2® or higher.

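### Continuous labs other than HbA1c: the treatment-only rank ANOVA leaves out the baseline value already collected and states only a p-value between arms; a ranked baseline covariate is a free, modest improvement

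*SAP*

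**What the plan says.** SAP 4.3.2 gives the lab default: "For continuous lab measurements, an analysis of variance (ANOVA) on rank-transformed data will be used and p-values for the difference between dulaglutide and placebo" are to be reported unless another method is named. The model contains treatment only. Protocol 12.2.9.4 matches: "continuous laboratory measures will be analyzed using an ANOVA model on the rank-transformed data. The model includes treatment". Protocol 12.2.1 likewise promises only p-values: "an analysis of variance (ANOVA) on ranks will be used and p-values for the difference between the dulaglutide and placebo will be reported".

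For continuous responses expected to be normal, the same SAP section uses baseline: "The MMRM model will be used to analyze changes from baseline with the baseline value as the covariate". It also promises an LS mean difference with 95% limits. SAP 4.15.1 moves HbA1c to that model. Calcitonin, creatinine, eGFR, urine ACR and lipids stay with the rank ANOVA.

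The baseline values exist. Protocol 12.2.9.4 names the visits: "Baseline for calcitonin, ALT, and hemoglobin A1c, will be Visit 1 and for serum creatinine, urine ACR and lipids will be Visit 3". SAP 4.2 adds a fallback: "If baseline data are missing, the last measurement taken prior to this visit will be used for the baseline measurement".

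Lipids have a stated response: percent change, or change for the cholesterol ratio (SAP 4.17.3.1). For the other four analytes no section says what is ranked. SAP 4.17.3 refers to Section 4.2 for the method, but the method is in 4.3.2.

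A separate paragraph of SAP 4.3.2 gives variables expected to be non-normal a Wilcoxon test: "In addition, the Hodges-Lehman estimator of the treatment contrast will be provided". It mentions no CI.

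**The concern.** Three things are affected.

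- **Precision.** A lab has a pre-randomization reading of the same quantity. Leaving it out of the model discards information that is already paid for.
- **Interpretation.** A p-value from ranks does not show how large a shift has been excluded. For a safety lab that is usually the useful question when the test is not significant.
- **An open choice.** SAP 4.3.2 provides for visit values, change and percent change. For four analytes the choice is left for later, and the unadjusted test behaves quite differently under each.

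**Working it through.** **1. What each route delivers**

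| Variables | Response | Baseline term | Stated between-arm output |
|---|---|---|---|
| HbA1c (SAP 4.15.1, 4.3.2) | change | yes | LS mean difference, 95% limits, p |
| Lipids (SAP 4.17.3.1, Protocol 12.2.9.4) | percent change; change for the ratio | no | p; possibly Hodges-Lehmann for triglycerides, no CI |
| Calcitonin, creatinine, eGFR, ACR | not stated | no | p |

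Triglycerides are the only lab that the SAP calls non-normal, so they may fall under the Wilcoxon paragraph.

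**2. Inputs.** The documents give no lab SD, effect size, power or correlation, so there is no planned figure to reproduce. From the documents: about 9600 patients randomized 1:1 (4800 per arm) and 2-sided alpha 0.05. Assumed: correlation r = 0.4, 0.6 or 0.8 between baseline and follow-up; equal variances; 3000 to 4800 measured per arm.

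**3. The planned test is a Wilcoxon test.** With two arms, F = (N−2)z²/(N−1−z²), where z is the tie-corrected Wilcoxon statistic. On tied data with N = 9600, F = 3.6455 both ways, with p = 0.05625 and 0.05626. SAP 4.3.2 therefore attaches an estimate to one form of the test and none to the other.

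**4. Variance removed by baseline.** Unranked, the share is r² for the visit value and (1−r)/2 for change. On ranks, convert each correlation ρ with baseline, in absolute size, to (6/π)·asin(ρ/2) and square it. Here ρ = r for the visit value and √((1−r)/2) for change.

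| r | Visit value, unranked | Visit value, ranks | Change, unranked | Change, ranks |
|---|---|---|---|---|
| 0.4 | 16% | 14.8% | 30% | 28.1% |
| 0.6 | 36% | 33.9% | 20% | 18.6% |
| 0.8 | 64% | 61.8% | 10% | 9.2% |

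**5. Detectable difference, 90% power, in SD (normal theory).** The formula is (1.960 + 1.282)·√(2/n), multiplied by √(2(1−r)) for change or √(1−r²) with baseline.

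| n per arm | Visit value | Change, r = 0.4 / 0.6 / 0.8 | With baseline, r = 0.4 / 0.6 / 0.8 |
|---|---|---|---|
| 4800 | 0.066 | 0.073 / 0.059 / 0.042 | 0.061 / 0.053 / 0.040 |
| 3000 | 0.084 | 0.092 / 0.075 / 0.053 | 0.077 / 0.067 / 0.050 |

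**6. Simulated power.** Lognormal marker, shift 0.06 SD on the log scale, r = 0.4, without and then with ranked baseline:

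- 4800 per arm, in repeated runs: visit value 81–84% to 87–91%; change 73% to 83–86%.
- 3000 per arm, in one run: visit value 59% to 66%; change 50% to 62%.
- Under no effect, rejection was 3.5 to 6.2% for all models (simulation SE 0.7 points).

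The choice of response matters without baseline. With 500 per arm and a 0.15 SD shift, the treatment-only rank test had 64% power on the visit value and 47% on change at r = 0.3, but 67% and 95% at r = 0.8. Rank ANCOVA on the visit value had 68% and 97%.

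**7. Which estimate survives ties.** Suppose 30% of placebo values sit at a reporting limit (assumed) and the shift is 0.06 SD.

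- The floor share on dulaglutide is Φ(−0.524 − 0.06) = 0.28, so 0.30 × 0.28 = 8.4% of between-arm pairs differ by exactly zero.
- The probability that dulaglutide exceeds placebo, ties counted half, is about Φ(0.06/√2) = 0.517. Negative differences are then about 1 − 0.517 − 0.042 = 0.441 of pairs, and zeros run from there to 0.525.
- The Hodges-Lehmann 95% limits are the pairwise differences at quantiles 0.5 ± 1.96·√(9601/(12·4800²)) = 0.488 and 0.512. Both fall among the zeros, so the result is 0 [0, 0].
- The test statistic is about 0.017/0.0059 = 2.9, which is significant.

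Simulation agrees: the interval collapsed in 97 to 100% of trials, while about 80% had p < 0.05.

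**The case against.** The case for leaving the plan alone has real content.

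- **A covariate rule exists.** SAP 4.3.1 admits a baseline covariate in the CSR when a factor is both clinically and statistically imbalanced, and the primary Cox model is treatment-only too. This does not fill the gap. A rule triggered by imbalance supplies no prespecified baseline term, and a first cardiovascular event has no pre-randomization reading of itself to adjust for.
- **The gain is small and rests on assumptions.** This stands. If change is ranked and r = 0.8, simulated power at 4800 per arm is 99% with or without baseline.
- **Some of it is covered.** Per-arm descriptive statistics in SAP 4.3.2 and Protocol 12.2.1 may extend to labs, and naming baseline visits points towards change. Neither is a between-arm estimate with a CI or a stated response.
- **Hodges-Lehmann for every lab would fail.** This also stands, as step 7 shows. With 30% tied, an interval computed after regression on baseline contradicted the rank ANCOVA p-value in 68 to 78% of trials.

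Because calcitonin is monitored for C-cell effects (Protocol 10.2.2.3.3.1), a reader might infer a gap in thyroid safety assessment. The documents do not support that. The upper tail is handled by the repeat-measurement algorithm above 35 pg/mL (Protocol 10.2.2.3.3.2), and thyroid outcomes are adjudicated and reported with incidence rates (SAP 4.17.1.2). Calcitonin is only one example of where an interval would help.

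**Conclusion.** The point holds as a free improvement of minor priority. For continuous labs other than HbA1c, the treatment-only rank ANOVA gives up precision that the collected baseline would return: about 15 to 62% of rank variance for the visit value, or 9 to 28% for change, over r = 0.4 to 0.8. The correlation, the numbers measured per visit and the 0.06 SD shift are assumptions. At about 4800 per arm the absolute gain is modest. The unnamed response and the wrong cross-reference are clarifications that accompany the main point.

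A reader might infer that the planned test is invalid. It is not: rejection under no effect was close to 5% with and without baseline. Alpha-controlled endpoints, adjudicated thyroid events, the calcitonin algorithm, the ACR shift tables and categorical comparisons, and the renal time-to-event components are unaffected. Nor is a protocol amendment needed. Protocol 12.2.1 reserves amendments for changes to a principal feature and lets other changes of method sit in the SAP.

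**What to change.** Change SAP 4.3.2 and 4.17.3 only.

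1. **Model.** Replace the rank ANOVA with a rank ANCOVA for all continuous labs that use it, including lipids: rank of response on treatment plus rank of that analyte's baseline. Values below a reporting limit share the lowest rank. Use the baseline visit in Protocol 12.2.9.4 with the SAP 4.2 fallback; eGFR takes the baseline of its creatinine.
2. **Clarifications.** Name the ranked response for calcitonin, creatinine, eGFR and ACR (for example, the visit value). Lipids keep theirs. Correct the reference in 4.17.3 from Section 4.2 to 4.3.2.
3. **Estimate with 95% CI.** Use the Hodges-Lehmann shift only for analytes without a material share of values at a reporting limit. Compute it after regression on baseline, or label it unadjusted, because it can then disagree with the adjusted p-value. Where values are tied at a floor, as may occur for calcitonin or ACR, report the probability that a dulaglutide value exceeds a placebo value, ties counted half, labelled unadjusted if baseline is not used.

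The cost is SAP wording and small programming changes, with no new data. Where the visit value is the response, patients with no pre-randomization value leave that analyte's model. Where change is the response nobody more is lost, because SAP 4.3.2 already imposes inclusion rules "plus the additional constraint that the patient has a baseline measurement of the variable"; SAP 4.17.3.1 requires the same for lipids.
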